ALLERGAN – CONFIDENTIAL

The following contains confidential, proprietary information which is the property of Allergan

STUDY TITLE

An Observational, Prospective Post-Marketing Surveillance Program to Evaluate the Safety Profile of Intravitreal Ozurdex[®] in the Treatment of Visual Impairment Due to Diabetic Macular Edema by Actively Identifying and Evaluating the Occurrence of Adverse Events and Serious Adverse Events Information

Version 1.0, DATE: 09 SEPTEMBER 2016

1

Post-Marketing Surveillance Program Information

| Title | An Observational, Prospective Post-Marketing Surveillance | |
|----------------------------------|--|--|
| | Program to Evaluate the Safety Profile of Intravitreal | |
| | Ozurdex [®] in the Treatment of Visual Impairment due to | |
| | Diabetic Macular Edema by Actively Identifying and | |
| | Evaluating the Occurrence of Adverse Events and Serious | |
| | Adverse Events information | |
| Protocol version identifier | | |
| | 1.0 | |
| Date of last version of protocol | 09 September 2016 | |
| Active substance | Dexamethasone | |
| Medicinal product | Ozurdex [®] is an intravitreal implant containing 0.7 mg (700 | |
| _ | mcg) dexamethasone in the Novadur [®] solid polymer | |
| | sustained-release drug delivery system | |
| | | |
| Product reference | Ozurdex [®] intravitreal implant | |
| Troduct reference | Szardok marandar miplan | |
| Marketing authorization | Allergan (North America) | |
| holder | [name] | |
| | [name] | |
| | 92612 | |
| | | |
| | | |
| | | |
| Research question and | The objective of this PMS program is to evaluate the safety | |
| abioativos | The objective of this Pivis program is to evaluate the safety | |
| objectives | profile of Ozurdex by actively identifying and evaluating | |
| | the occurrence of AEs and SAEs for 1 year period in adult Ladian matients $(> 19 \text{ means of } > 1 matter in the second of t$ | |
| | indian patients (\geq 18 years of age) who will be receiving at | |
| | least one intravitreal Ozurdex [®] injection for the treatment of | |
| | visual impairment due to DME. | |
| Country of study | India | |
| Author | | |
| | | |
| | | |
| | | |
| | | |

Marketing authorization holder

| Marketing authorization | Allergan (North America) | |
|-------------------------|--------------------------|--|
| holder (MAH) | [name] | |
| | [name] | |
| | 92612 | |
| | | |
| | | |
| MAH contact person | | |
| | | |
| | | |

Rationale and background: Ozurdex[®] (dexamethasone intravitreal implant) is a corticosteroid indicated for the treatment of macular edema following branch retinal vein occlusion (BRVO) or central retinal vein occlusion (CRVO); non-infectious uveitis affecting the posterior segment of the eye; and DME. Ozurdex[®] is an intravitreal implant containing 0.7 mg (700 mcg) dexamethasone in the Novadur[®] solid polymer sustained-release drug delivery system.

India is second to China in having the maximum number of diabetics. This significant proportion of diabetes in India indicates an increase in diabetic retinopathy or DME cases. The increase of such cases is directly proportional to the duration of diabetes.

As a part of Allergan's commitment to the Regulatory Authority of India, this PMS program is planned to be conducted to collect safety information from Indian patients who will be receiving intravitreal Ozurdex[®] injection for the treatment of visual impairment due to DME.

Research question and objectives: The objective of this PMS program is to evaluate the safety profile of Ozurdex[®] by actively identifying and evaluating the occurrence of AEs and SAEs for 1 year period in adult Indian patients (≥ 18 years of age) who will be receiving at least one intravitreal Ozurdex[®] injection for the treatment of visual impairment due to DME.

Study design: This is an observational, prospective PMS program to evaluate the safety profile of intravitreal Ozurdex[®] by actively identifying and evaluating the occurrence of AEs and SAEs information.

This study focuses on timely detection and characterization of serious and non-serious adverse events (AEs) including important identified and potential risks and AEs of special interest observed with intravitreal Ozurdex[®] injection for the treatment of visual impairment due to diabetic macular edema (DME) in the Indian population during usual clinical practice.

Ozurdex[®] (dexamethasone intravitreal implant) is a corticosteroid indicated for the treatment of macular edema following branch retinal vein occlusion (BRVO) or central retinal vein occlusion (CRVO); non-infectious uveitis affecting the posterior segment of the eye; and DME. Ozurdex[®] is an intravitreal implant containing 0.7 mg (700 mcg) dexamethasone in the Novadur[®] solid polymer sustained-release drug delivery system¹.

Diabetic macular edema

Diabetic eye disease (retinopathy) can damage the small blood vessels of the eye. Fluid leaking from these blood vessels may cause the central part of the retina (the macula) to swell. This is called DME. Diabetic macular edema is the most common cause of vision loss in people who have diabetes². Diabetic macular edema affects 20% of patients with diabetic retinopathy³. Diabetic macular edema is characterized by capillary leakage, fluid accumulation, and macular thickening following breakdown of the blood retinal barrier⁴. Inflammation plays a significant role in DME pathogenesis because the breakdown of the blood retinal barrier involves expression of inflammatory factors⁵ including vascular endothelial growth factor (VEGF), intercellular adhesion molecule-1, interleukin-6, monocyte chemotactic protein-1, leukostasis⁶ and alterations in endothelial tight junction proteins⁷.

India is second to China in having the maximum number of diabetics⁸. The International Diabetes Federation projects the increase in number of people with diabetes in India from 65.1 million in 2013 to 109 million in 2035⁹. This significant proportion of diabetes in India indicates an increase in diabetic retinopathy or DME cases. One risk factor for the development of diabetic retinopathy is hypertension associated with diabetes. The increase of such cases is directly proportional to the duration of diabetes. Proliferative diabetic retinopathy was seen in patients with 11 years of diabetes. Severe diabetic retinopathies were observed in 100% of patients with 25 years of diabetes¹⁰.

Laser photocoagulation, considered for a long time as the main treatment option for DME, may lead to paracentral deficits of the visual field and reduced color vision and sensitivity to contrast¹¹. For these reasons, intravitreal therapies with anti-VEGF have been considered as an efficient treatment strategy for patients affected by DME¹². Intravitreal corticosteroids may be useful in the treatment of DME because they block production of VEGF and other inflammatory mediators¹³, inhibit leukostasis¹⁴, and enhance the barrier function of vascular endothelial cell tight junctions¹⁵.

Ozurdex[®] produces significant improvements in best-corrected visual acuity (BCVA) and central macular thickness from the third day of implant in patients with DME, and this improvement will be sustained until the third month¹⁶.

Retinal vein occlusion

Ozurdex[®] is also indicated for the treatment of macular edema following BRVO or CRVO. The efficacy of Ozurdex[®] for the treatment of macular edema following BRVO or CRVO was assessed in two multicenter, double-masked, randomized, parallel studies. Following a single injection, Ozurdex[®] demonstrated the following clinical results for the percentage of patients with \geq 15 letters of improvement from baseline in BCVA.

In each individual study and in a pooled analysis, time to achieve ≥ 15 letters (3-line) improvement in BCVA cumulative response rate curves were significantly faster with Ozurdex[®] compared to sham (p < 0.01), with Ozurdex[®]-treated patients achieving a 3-line improvement in BCVA earlier than sham-treated patients.

The onset of a ≥ 15 letter (3-line) improvement in BCVA with Ozurdex[®] occurs within the first two months after implantation in approximately 20% to 30% of subjects. The duration of effect persists approximately one to three months after onset of this effect¹.

Posterior segment uveitis

Ozurdex[®] is also indicated for the treatment of non-infectious uveitis affecting the posterior segment of the eye. The efficacy of Ozurdex[®] was assessed in a single, multicenter, masked, randomized study of 153 patients with non-infectious uveitis affecting the posterior segment of the eye. After a single injection, the percentage of patients reaching a vitreous haze score of 0 (where a score of 0 represents no inflammation) was statistically significantly greater for patients receiving Ozurdex[®] versus sham at week 8 (primary time point) (47% versus 12%). The percentage of patients achieving a 3-line improvement from baseline BCVA was 43% for patients receiving Ozurdex[®] versus 7% for sham at week 8¹.

Mechanism of action

Dexamethasone, a corticosteroid, has been shown to suppress inflammation by inhibiting multiple inflammatory cytokines resulting in decreased edema, fibrin deposition, capillary leakage and migration of inflammatory cells.

Pharmacokinetics

Plasma concentrations were obtained from 21 patients with macular edema due to BRVO and CRVO, and 21 patients with DME prior to dosing and at 4 to 5 additional post-dose timepoints on Days 1, 7, 21, 30, 45, 60, and 90 following the administration of the first intravitreal implant containing 0.7 mg dexamethasone. In retinal vein occlusion and DME patients, the majority of plasma dexamethasone concentrations were below the lower limit of quantitation (LLOQ = 50 pg/mL). Plasma dexamethasone concentrations from 12% of samples were above the LLOQ, ranging from 52 pg/mL to 102 pg/mL. Plasma dexamethasone concentration did not appear to be related to age, body weight, or sex of patients.

No metabolites were observed in an *in-vitro* metabolism study following the incubation of [¹⁴C]-dexamethasone with human cornea, iris-ciliary body, choroid, retina, vitreous humor, and sclera tissues for 18 hours.

Rationale of the study

As a part of Allergan's commitment to the Regulatory Authority of India, this post-marketing surveillance (PMS) program is planned to be conducted to collect safety information from Indian patients who will be receiving intravitreal Ozurdex[®] injection for the treatment of visual impairment due to DME.

The important identified risks and important potential risks for Ozurdex[®] are consistent with the current benefit-risk profile.

8. Research question and objectives

The objective of this PMS program is to evaluate the safety profile of Ozurdex[®] by actively identifying and evaluating the occurrence of AEs and serious adverse events (SAEs) for 1 year period in adult Indian patients (\geq 18 years of age) who will be receiving at least one intravitreal Ozurdex[®] injection for the treatment of visual impairment due to DME.

9. Research methods

9.1. Study design

This is an observational, prospective PMS program to evaluate the safety profile of intravitreal Ozurdex[®] by actively identifying and evaluating the occurrence of AEs and SAEs information.

Investigators will be trained on the conduct of the study by the Clinical Research Associate (CRA).

On the Visit 1/Baseline visit, an informed consent would be provided to the patients for obtaining consent to share the collected safety information for research purposes. No further visits are planned as it is at the discretion of the treating physician/investigator to schedule a follow-up (clinic visit/telephonic contact) with the patients. Refer to Annex 1 for sample informed consent form (ICF).

Following the signature on the ICF, the basic required information will be collected at Visit 1 by the study physician in a pre-designed case report form (CRF). The information collected at Visit 1 includes, patient demography characteristics, medical history, concomitant medications, ophthalmic history, concomitant ophthalmic medications, the date of the last intravitreal Ozurdex[®] injection if applicable, date of the present intravitreal Ozurdex[®] injection and AEs/SAEs at baseline if any (and the dates of AE/SAEs if available). Refer to Annex 1 for sample CRF.

No medication will be provided as part of the study as this is non-interventional and confers to usual clinical practice. However, the marketed intravitreal Ozurdex[®] injection could be administered to the patient at the discretion of the treating physician/investigator if he/she considers that it would be beneficial for the patient. The injection can be provided by the physician/investigator either in the same visit when informed consent was signed or in the subsequent visit. The date of the injection given will be recorded. Refer to Annex 1 for the Prescribing Information of Ozurdex[®] Intravitreal Implant for detailed Ozurdex[®] administration procedure. Patients who do not receive the injection will be replaced.

During the subsequent follow-up visits/telephonic contact, the study investigator will begin by querying for AEs by asking each subject a general, non-directed question such as "How have you been feeling since the last visit?" Investigator collects the information pertaining to AEs/SAEs and the dates of AE/SAEs if available, date of the last intravitreal Ozurdex[®] injection and other details entailing the safety information as mentioned in the pre-designed CRF.

For description of the study process, please see Figure 1.

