Regarding marketed medicinal products: a response to a drug which is noxious and unintended and which occurs at doses normally used in man for prophylaxis, diagnosis, or therapy of diseases or for modification of physiological function. All noxious and unintended responses to a medicinal product related to any dose should be considered ADRs.

Severity of AE

A clinical determination will be made of the intensity of an AE. The severity assessment for an AE must be completed using the following definitions as guidelines:

| Mild | Awareness of sign or symptom, but easily tolerated. |
|----------|---|
| Moderate | Discomfort enough to cause interference with usual activity |
| Severe | Incapacitating with inability to work or do usual activity. |

All AEs/SAEs/ADRs that occur during and/or after administration of the product during the follow-up period will be collected regardless of causal relationship to the product.

All AEs, SAEs and ADRs (serious or not) should be recorded on the study CRF. All AEs, SAEs and ADRs should be reported to Allergan global safety team at

Each participating investigator will be trained on the recording of AEs/SAEs/ADRs. The physician or site staff should instruct patients to report SAEs and reportable AEs from the time of enrollment through end of follow-up or early discontinuation from the study during this time period.

Reporting of the events:

Each patient interview will begin with simple open-ended questions and questions designed to collect information regarding specific outcomes of interest. If a patient is seen by a non-study physician, the study physician and/or trained site staff should make every effort to follow-up with the relevant concerned health care provider to obtain all information necessary for the accurate reporting of the event in a timely manner.

All AEs, SAEs and ADRs (serious or not) should be recorded on the study CRF. All events reported on the CRF by the study physician will be confirmed by medical record review and/or direct follow-up with the treating physician. In the event of a death, cause of death will be recorded.

Since this is a non-interventional study, the following types of events should be sent to Allergan global safety team: AEs, SAEs, non-serious ADRs, pregnancies and special situations (lack of effect, overdose, medication error, misuse, abuse, off-label use, use while breastfeeding or occupational exposure).

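### The one-year active-surveillance objective rests on no assured contact after Visit 1, so the AE/SAE frequency depends on who happens to return

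*Protocol*

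**What the plan says.** **Objective.** Section 8 commits the programme to "actively identifying and evaluating the occurrence of AEs and serious adverse events (SAEs) for 1 year period in adult Indian patients", and the title also describes the identification as active. Section 7 adds a focus on AEs "including important identified and potential risks and AEs of special interest".

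**Follow-up.** After Visit 1, Section 9.1 says "No further visits are planned as it is at the discretion of the treating physician/investigator to schedule a follow-up", by clinic visit or telephone. Sections 9.1 and 9.2 describe what is collected at such contacts: AEs, SAEs and ADRs with dates if available, the last injection date, medication given for the events, and other safety details on the CRF. Section 9.8 refers to a final follow-up assessment and Section 11.1 to an end of follow-up, but neither point is defined.

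**Interview.** Section 9.1 has the investigator open by "asking each subject a general, non-directed question such as" one about how the patient has felt since the last visit. Section 11.1 has each interview begin with "simple open-ended questions and questions designed to collect information regarding specific outcomes of interest". The protocol text does not list those outcomes.

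**Analysis and limitations.** Section 9.7 calculates AE/SAE frequency across study participants, censors patients who do not return, and imputes nothing. Section 9.9 accepts that, without mandated visits, a large amount of data may be missing.

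**The concern.** An active one-year objective needs some means of learning each patient's status at the end of the observation period. Here that depends on each investigator's habits and each patient's decision to come back. A patient with no post-injection contact contributes no event, and the listed variables give nothing to separate that silence from a year without events. Censoring needs a date, and none is listed. The final report goes to the agency for expert committee evaluation (Section 12.1), so the frequencies should be interpretable. No later analysis can recover a contact that was never made.

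**Working it through.** The protocol gives no figure to reproduce. It has no formal sample size calculation, no hypothesis test, and no assumed event rate or loss to follow-up. The check is a comparison of sections, followed by an illustration.

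**Comparison**

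1. Section 8 requires active identification over one year. Section 9.1 fixes no contact after Visit 1, and no other section sets a number, an interval or a closing contact. An injected patient who is never contacted again is therefore within protocol.
2. Sections 9.2 and 9.3 list demography, histories, medications, pregnancy, event details and injection dates. They list no date of last contact and no end-of-follow-up status. The sample CRF in Annex 1 is not at hand and may hold more.
3. Section 9.4 names medical records as the data source but sets no time at which they must be reviewed. The record review in Section 11.1 confirms events already reported on the CRF. It does not search for unreported ones.

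**Illustration of direction**

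Inputs: N = 250 (Section 9.5). Assumed: a true one-year frequency of 10%, hence 0.10 × 250 = 25 patients with the event; a share contacted of 80%, 60% or 40%; and complete ascertainment in contacted patients. With u uncontacted patients at risk r, the number found is 25 − u × r.

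| Contacted | u | r (assumed) | Found | Found / 250 | Found / contacted |
|---|---|---|---|---|---|
| 200 (80%) | 50 | 10% | 25 − 5 = 20 | 8.0% | 10.0% |
| 150 (60%) | 100 | 10% | 25 − 10 = 15 | 6.0% | 10.0% |
| 100 (40%) | 150 | 10% | 25 − 15 = 10 | 4.0% | 10.0% |
| 200 (80%) | 50 | 5% | 25 − 2.5 = 22.5 | 9.0% | 11.3% |
| 150 (60%) | 100 | 5% | 25 − 5 = 20 | 8.0% | 13.3% |
| 100 (40%) | 150 | 5% | 25 − 7.5 = 17.5 | 7.0% | 17.5% |

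If contact is unrelated to having an event (r = 10%), the frequency over all participants is too low and the frequency among contacted patients is right. If patients with symptoms return more often (r = 5%), the first is still too low, though by less, and the second is too high.

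**Illustration of precision**

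Even with contact unrelated to events, information is lost. If no event is seen, the one-sided 95% upper bound is 1 − 0.05^(1/n): 1.19% for n = 250, 1.49% for 200, 1.98% for 150 and 2.95% for 100. The chance of seeing at least one case of a 1% event, 1 − 0.99^n, falls from 91.9% to 86.6%, 77.9% and 63.4%.

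**The case against.** The best defence is that discretionary follow-up belongs to a non-interventional study of usual practice. The protocol discloses the consequence in Section 9.9, censors non-returners in Section 9.7, and may leave the exact denominator to an SAP that is not shown. Much of this stands. The lack of mandated care visits is no fault, and the denominator is not raised here as missing. But disclosure does not supply the data, and a denominator chosen later cannot tell a silent patient from an event-free one. A telephone call or chart check mandates no care. Section 9.1 already foresees telephone contact, and Section 9.4 already relies on medical records.

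The defence also defeats several stronger readings that a reader might infer:

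- *No follow-up is planned at all.* Clinic and telephone follow-up is foreseen and its content described. It is simply not assured.
- *Section 9.1 relies on the open question alone and conflicts with Section 11.1.* In Section 9.1 the open question comes first and CRF safety details follow. Section 11.1 also starts with open questions and adds directed ones, so a site can comply with both. Section 9.1 merely omits the directed part.
- *Special-interest events will be the most under-counted.* This is a risk, not a demonstrated result. Section 11.1 calls for directed questions, and the CRF is not at hand.
- *Telling sites to "instruct patients to report SAEs and reportable AEs from the time of enrollment through end of follow-up" narrows what is collected.* That is an instruction to patients. Section 11.1 collects all AEs regardless of causality, so the phrase is an editorial matter.

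**Conclusion.** The point holds as a gap in ascertainment. Nothing in the protocol assures that any patient's status is known after Visit 1, and the listed variables do not record when each patient was last known to be event-free. The resulting frequencies depend on who returns.

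The size of the bias cannot be stated, because the protocol gives no expected share of patients with follow-up. The percentages in the table rest on assumed event rates and contact shares and show direction only. A reader might take the true frequency multiplied by the share contacted as a ceiling on what the study would report. It is not one: that product assumes equal risk in uncontacted patients, and if symptomatic patients return more often the reported figure lies above it.

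This is a worthwhile and inexpensive improvement. It does not invalidate the design. The mismatch between the interview descriptions in Sections 9.1 and 11.1 is secondary.

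**What to change.** **Main change, Section 9.1.** Add one closing telephone contact or chart check per patient at the end of that patient's follow-up, and state when that end falls. Record the date, vital status, and AEs/SAEs since the last contact. Where only the chart is available, record the date of its last entry as well, because a chart reviewed late says nothing about the time after the patient stopped attending. Add these items to Section 9.3 and the CRF. State that no care visit or procedure is mandated.

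**Alignment.** Have Section 9.1 say that the open question is followed by Section 11.1's questions on specific outcomes of interest. Name those outcomes in the protocol or CRF, and have them checked against the medical record named in Section 9.4.

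**Editorial.** In Section 11.1, tell patients to report all AEs, in line with the collection rule in the same section.

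**Cost.** One short call or chart check per patient, 250 / 20 = 12.5 per site on average, and a few CRF fields. The downside is a little site time; the study stays non-interventional.
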